4.1 Preface

Peanut allergy (PA) is a common and potentially life threatening condition for which the only current approved management involves strict dietary avoidance. Oral immunotherapy (OIT) is a promising investigational treatment option for this condition, but the widespread clinical use of OIT has been limited by factors including the high rate of adverse events (AEs), including anaphylaxis. Published studies demonstrating the efficacy of OIT in children with peanut allergy, many of which reported high rates of dropout and AEs, have all used peanut products produced by roasting methods, while published data have demonstrated that boiling peanut results in reduced allergenicity without reduction to immunogenicity. In this pilot study, we plan to compare the use of boiled peanut OIT to published data on roasted peanut OIT in children with peanut allergy and hypothesize that the subjects treated with a novel regimen of boiled peanut will demonstrate lower rates of adverse events while demonstrating similar immunologic markers of peanut desensitization and tolerance.

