We seek to identify a means of accomplishing peanut desensitization while decreasing the rate of treatment related AEs. It has been shown that standard roasting methods of peanut preparation can play a significant role in increasing the undesirable allergenic properties of peanuts.¹⁷ It has also been demonstrated that peanut antigen stimulation of peripheral blood T lymphocytes is unaffected by various heating methods, which is necessary for induction of tolerance.¹⁸ An additional study confirms the findings of extended boiling resulting in reduction of peanut allergenicity while preserving the effect on T cell reactivity.¹⁹ A group recently reported a series of 4 subjects with peanut allergy who were treated with daily doses of boiled peanut, one of which subsequently transitioned to raw peanut. All subjects demonstrated lower IgE reactivity to boiled peanut compared to control suggesting that in vivo findings correlate with the prior in vitro data.²⁰

While OIT is a promising therapy, we hypothesize that by treating peanut allergic subjects with a peanut product of reduced allergenicity but preserved T cell reactivity, we will be able to desensitize these subjects to a target maintenance dose of peanut protein with reduced rates of allergen associated AEs, while preserving immunologic effects that will promote tolerance. This will confirm that the immunologic changes produced by roasted peanut OIT can be replicated more safely using boiled peanut. If successful, such a therapy will decrease the number of subjects that must discontinue this treatment due to related AEs, and offer a potentially important therapy for this life threatening condition. Improved safety of this intervention may also allow for higher treatment doses to be used, may allow inclusion of more severely allergic subjects excluded from previous trials, and possibly increase the likelihood for attainment of permanent tolerance with sustained unresponsiveness, rather than perpetuating the need for continual daily dosing. This will likely result in the eventual inclusion of BPOIT in general Allergy/Immunology practice as a treatment for peanut allergy. We suspect this therapy will improve quality of life as measured by validated questionnaires as well as, or better than, roasted peanut oral immunotherapy.²⁸

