4.1 Overall Design

We will perform a phase 1 clinical trial utilizing oral immunotherapy with powder derived from boiled peanut. Our hypothesis is that the subjects treated with this novel regimen of boiled peanut will demonstrate lower rates of adverse effects while demonstrating similar immunologic markers of peanut desensitization and possible tolerance in comparison to published data on subjects treated with OIT utilizing roasted peanut product.

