6.1 General Study Design and Plan

This study is a prospective single-arm Phase 1 clinical trial providing proof of concept data on boiled peanut oral immunotherapy (OIT) for the treatment of peanut allergy in children. There will be no randomization or blinding.

The primary endpoint of rate of response to treatment will be performed as a one-sample superiority test compared to a null hypothesis rate of 20%. Assessments of within-patient changes in maximum tolerated dose, cumulative tolerated dose, immune response, and quality of life will be performed with two-sided tests. Comparisons of adverse event rates will be made to data in published studies of roasted peanut OIT; these comparisons will be descriptive with no hypothesis testing.

For study flow chart, refer to study protocol section 1.2 Study Schema.

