10.2 Analysis of Secondary Efficacy Endpoints

Secondary efficacy endpoints consist of changes in continuous or ordinal variables from the

enrollment/baseline, initial OFC, or initial dose escalation visit to the final study visit. The primary analyses of the change endpoints will be performed using Wilcoxon signed rank tests, with null hypotheses of no change, versus two-sided alternative hypotheses at a significance criteria of 0.05. Missing data will not be imputed, and complete cases only will be analyzed (see section 8.4). Due to the small sample size, visual assessments of the symmetry assumptions of the Wilcoxon signed rank tests are unlikely to be definitive, and p-values for Sign tests under the same null hypotheses and significance criteria will also be presented as sensitivity analyses. The summary statistics will be reported as described in section 9.

Highest tolerated dose and cumulative tolerated dose. Changes in highest tolerated dose and cumulative tolerated dose from initial OFC to the peanut protein arm of the exit DBPCFC will be analyzed as ordinal variables, using nonparametric tests. The analysis population will be the Efficacy Population. (Refer to mock Table 2.3.)

Serum markers of sensitization and tolerance to peanut. Changes in serum markers of sensitization and tolerance to peanut will be analyzed as continuous variables using nonparametric tests. The analysis population will be the Modified Efficacy Population for immune response. (Refer to mock Table 2.4.)

FAQLQ. Changes in FAQLQ subscale and summary scores will be analyzed as continuous variables using nonparametric tests. The percent of patients with change in summary score greater than or equal to the MID will be reported with 95% Clopper-Pearson exact confidence interval. Hypothesis testing will be performed for summary scores only. Parent and Teenager forms will be analyzed separately, and the analysis populations will be the Modified Efficacy Populations for FAQLQ-PF and FAQLQ-TF. (Refer to mock Tables 2.5 and 2.6.)

11 Safety Analyses

Safety analyses will be performed on the safety population unless otherwise specified. Summary statistics will be reported as described in section 9.

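### Serum markers are hypothesised to be similar to published roasted-peanut OIT, but the visible analysis sections test them only against no change from baseline

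*SAP*

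**What the plan says.** **The claim.** The SAP Preface (4.1) hypothesises that treated children "will demonstrate lower rates of adverse events while demonstrating similar immunologic markers of peanut desensitization and tolerance". Protocol 4.1 states the comparator, expecting "similar immunologic markers of peanut desensitization and possible tolerance in comparison to published data on subjects treated with OIT utilizing roasted peanut product"; Protocol 2.1 says much the same. Protocol 2.2 goes further: "This will confirm that the immunologic changes produced by roasted peanut OIT can be replicated more safely using boiled peanut". SAP 4.2, on the scope of the analyses, covers the immune response and announces a comparison with published roasted-peanut data.

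**The analysis.** SAP 9.2.2 defines each marker's change as the final minus the initial value. SAP 10.2 analyses the changes by "Wilcoxon signed rank tests, with null hypotheses of no change, versus two-sided alternative hypotheses at a significance criteria of 0.05", with Sign tests of the same null as sensitivity analyses. The title of Table 2.4 refers only to changes within the study.

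**The roasted comparison.** SAP 6.1 plans one for safety: "Comparisons of adverse event rates will be made to data in published studies of roasted peanut OIT". It is descriptive. SAP 11.1.2 names three published sources, for adverse event data only, and Table 3.3 is the matching output.

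**The concern.** The hypothesis and the analysis use different comparators. The hypothesis sets the boiled-peanut marker response beside the roasted one; the test sets it beside zero. Rejecting no change says that a marker moved, not that it moved as far as it does with roasted peanut. Failing to reject does not show that it moved less.

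The rationale is a product with reduced allergenicity and a preserved immune effect. The immunologic failure to look for is therefore a response that is real but weaker than with roasted peanut, and a test against zero is not built to find it. No interval is planned for the marker changes: SAP section 9 gives the median, quartiles and range, and the only confidence interval in SAP 10.2 is for the proportion reaching the quality-of-life threshold. A reader would have no planned basis for judging which roasted values the data are compatible with.

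The point is confined to the serum markers. The desensitized proportion is a separate matter.

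**Working it through.** **1. The plan's own figure.** The only stated power is for the responder endpoint: above 90% with N = 10, 80% against 20% (Protocol 9.2, SAP 7). Under the exact one-sided 0.05 rule of SAP 10.1, P(X ≥ 4 | 10, 0.2) = 0.121 is too large and P(X ≥ 5 | 10, 0.2) = 0.0328 is allowed. Power is P(X ≥ 5 | 10, 0.8) = 99.4%, so the figure holds. The documents give no power, margin or benchmark for the markers.

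**2. Logic, without numbers.** Let δ be the mean boiled change and ρ the mean roasted change. The hypothesis concerns δ relative to ρ. The planned null is δ = 0, and ρ appears nowhere in the analysis. The result therefore cannot bear on similarity, whatever the value of δ.

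**3. Illustration.** Assumptions, none from the documents: normally distributed changes; an exact signed-rank test; ρ from 1 to 3 SD of the within-child change. Ten pairs is the planned sample. Eight is an example of loss under the complete-case rule (SAP 8.4). Critical values, as the smaller rank sum: n = 10, ≤ 8 (two-sided level 0.0488); n = 8, ≤ 3 (0.0391). There were 100,000 simulated trials per case. Each cell is the chance of a significant result.

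| Assumed ρ (SD) | n = 10, δ = ρ/2 | n = 10, δ = ρ | n = 8, δ = ρ/2 | n = 8, δ = ρ |
|---|---|---|---|---|
| 1 | 28% | 79% | 19% | 61% |
| 1.5 | 55% | 98% | 39% | 92% |
| 2 | 78% | about 100% | 61% | 99% |
| 2.5 | 93% | about 100% | 80% | about 100% |
| 3 | 98% | about 100% | 92% | about 100% |

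For large ρ the test hardly separates a half-size from a full-size response. For ρ near 1 SD a half-size response usually misses significance, but a full-size one also misses in 100 − 79 = 21% of trials with 10 pairs and 100 − 61 = 39% with 8. Neither outcome identifies similarity.

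**4. What ten children can show.** The half-width of a t-based 95% CI for the mean change is t(0.975, n − 1)/√n, in SD units: 2.262/√10 = 0.72 for n = 10 and 2.365/√8 = 0.84 for n = 8. A formal one-sample t test that the boiled change exceeds half of a fixed roasted benchmark (one-sided 0.025, n = 10), if boiled truly equals roasted, has power of 29%, 56%, 80% and 99% for ρ = 1, 1.5, 2 and 3 SD. Unless ρ is about 2 SD or more, a descriptive comparison is the realistic aim.

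**The case against.** **The test fits the formal objective.** For the immune response, Protocol 3 and SAP 5.1 ask only what effect boiled peanut has, with markers measured at the start and end. Within-child change answers that, and Protocol 9.1 states no marker hypothesis. This stands, and it means the test is not wrong for the listed objective. It does not remove the mismatch: Protocol 4.1 presents similarity as the study's hypothesis, and SAP 4.2 puts a published-data comparison within the scope of the analyses.

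**A stronger reading is not supported.** A reader might infer that a significant change will be reported as equivalence with roasted OIT, or that a weaker response would pass unnoticed. No passage says that a significant change will be interpreted as similarity. SAP 8.5 calls secondary tests hypothesis-generating, and the confirming sentence in Protocol 2.2 is background text that is not tied to the marker test. The planned medians, quartiles and ranges will also show the size of the boiled effect, though without a roasted figure beside it.

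**The percentages rest on assumptions.** SAP 10.1 specifies exact methods for the primary endpoint only, SAP 9.2.2 uses plain differences whose distribution is unknown, and no document supports any one roasted effect size. This stands, so only the full range is informative.

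**A comparator may sit in the mock tables.** Appendix I was not available for this reading, so this cannot be excluded. SAP 6.1, SAP 11.1.2 and the table titles point the other way.

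**Published marker values may not be usable.** The documents contain none; Protocol Table 1 lists adverse events and dropouts. This stands and shapes the remedy.

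**Conclusion.** The concern holds in a limited form. The similarity hypothesis has no corresponding marker analysis in the visible plan, and a test against no change cannot supply one. That conclusion needs no distributional assumption. What follows is that a smaller immune response than with roasted peanut could be taken as support, not that it would be. How often a half-size response would be significant depends on an unknown: 28% to 98% with 10 pairs and 19% to 92% with 8, for assumed roasted effects of 1 to 3 SD, normal changes and an exact test. Severity is minor to moderate: the tests are already labelled non-confirmatory, and the trial is a ten-child proof of concept.

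**What to change.** Choose one of two changes, before the analysis.

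(a) In SAP 10.2 and Table 2.4, report each marker's change (peanut IgE, components, IgG4) with a 95% CI suited to the nonparametric analysis, for example a Hodges-Lehmann estimate with the interval obtained by inverting the signed-rank test. Where a published roasted-OIT change exists for the same marker, on the same scale and at a near time point, list it beside the estimate, from sources named in advance. Label the comparison descriptive, and state that a significant change from baseline does not show similarity.

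(b) Where no suitable published values exist, restate the aim as change from baseline in Protocol 2.1, 2.2 and 4.1 and SAP 4.1. Also limit the published-data comparison in SAP 4.2 so that it no longer covers the markers; otherwise the inconsistency remains there.

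Neither option needs new data, visits or children. Option (a) costs some work to find and check published values, which may not exist for every marker. The price of either is a more modest immunologic claim.

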4.2 Scope of the analyses

These analyses will assess the efficacy, safety, and tolerability of boiled peanut immunotherapy on the immune response to peanut protein, with comparison to published data on subjects treated with OIT utilizing a traditional roasted peanut product and will be included in the study report.

5 Study Objectives and Endpoints

5.1 Study Objectives

Primary objective. Determine the effect of boiled peanut immunotherapy on the immune response to peanut and demonstrate that the proportion of subjects successfully desensitized with boiled peanut OIT is not appreciably lower than the proportion of subjects successfully desensitized with roasted peanut OIT in published data.

Secondary objective. Compare the rate of adverse effects of boiled peanut oral immunotherapy to published data on roasted peanut oral immunotherapy.

5.2 Endpoints

Primary Endpoints. Response to treatment defined as ability to successfully consume a single dose of 300 mg or greater of peanut protein with no dose limiting symptoms at exit double blind placebo controlled food challenge (DBPCFC).

The highest dose of roasted peanut protein tolerated by the subject at exit DBPCFC will also be compared to the highest dose tolerated at baseline.

The effect of boiled peanut immunotherapy on the immune response to peanut will be evaluated via specific serum markers of sensitization and tolerance to peanut.

- Levels of serum specific peanut IgE, with higher levels associated with greater likelihood of clinical reaction on exposure to peanut protein.

- Peanut protein component panel, to determine the presence of high levels of sensitivity to peanut proteins known to be associated with severe systemic reactions (Arah 1,2, 3) versus mild reactions (Arah8)
- Levels of peanut specific serum IgG4, with higher levels associated with increased tolerance to peanut protein

These markers will be evaluated at baseline and the conclusion of the study.

Secondary Endpoints. The rate of adverse events in the subjects receiving boiled peanut oral immunotherapy. Possible adverse events include: side effects of treatment defined as oral itching, rhinorrhea, conjunctivitis, urticaria, angioedema, abdominal upset, vomiting, diarrhea, cough, wheeze, or anaphylaxis

- Adverse events will be recorded in terms of the percentage of subjects with adverse events on initial escalation day and at dose escalation visits by CRU staff.
- Adverse events will also be recorded in terms of overall percentage of home doses that result in adverse reaction, with data compiled from home logs.

The adverse reactions will be graded in severity and the treatment required will be recorded.

Validated, age-specific, food-related quality-of-life surveys before and after peanut oral immunotherapy will be completed by all patients/families.

6 Study Methods

6.1 General Study Design and Plan

This study is a prospective single-arm Phase 1 clinical trial providing proof of concept data on boiled peanut oral immunotherapy (OIT) for the treatment of peanut allergy in children. There will be no randomization or blinding.

The primary endpoint of rate of response to treatment will be performed as a one-sample superiority test compared to a null hypothesis rate of 20%. Assessments of within-patient changes in maximum tolerated dose, cumulative tolerated dose, immune response, and quality of life will be performed with two-sided tests. Comparisons of adverse event rates will be made to data in published studies of roasted peanut OIT; these comparisons will be descriptive with no hypothesis testing.

For study flow chart, refer to study protocol section 1.2 Study Schema.

6.2 Inclusion-Exclusion Criteria and General Study Population

Inclusion Criteria
Age 1-16 years
History of immediate hypersensitivity reaction to peanut or a high level of suspicion based on testing at the discretion of the investigator
Evidence of IgE mediated peanut hypersensitivity within a 12 month period of study enrollment
SPT with wheal/flare of at least 3 x 6 mm
and/or
Peanut specific IgE >0.35 kU/L

Abbreviations: SPT, skin prick test

In addition, the individual's parent or guardian must provide signed and dated informed consent and the individual must provide signed and dated assent when appropriate. The individual and parent or guardian must agree to comply with all study procedures and the individual must have the ability to take oral medication.

Exclusion Criteria
History of life threatening peanut anaphylaxis
Asthma requiring more than medium dose ICS
Prior participation in OIT, SLIT or EPIT
Oat allergy
Cardiovascular Disease
Use of beta-blockers (oral), angiotensin converting enzyme inhibitors, angiotensin receptor blockers, or calcium channel blockers
Use of steroid medications in the following manners:
Daily oral steroid dosing for greater than 1 month during the past year OR
Burst or steroid course in the past 3 month before inclusion OR
Greater than 2 bursts oral steroid courses in the past year of at least 1 week duration
Pregnancy or lactation
Eosinophilic Gastrointestinal Disease
History of food protein-induced enterocolitis (FPIES)
History of developmental delay or speech delay that precludes age-appropriate communication, in the opinion of the investigator

Abbreviations: ICS, inhaled corticosteroid, OIT, oral immunotherapy, SLIT, sublingual immunotherapy, EPIT, epicutaneous immunotherapy

A history of life-threatening anaphylaxis is defined as a reaction involving respiratory failure, hypotension or neurologic compromise. Medium dose ICS is defined by the National Heart, Lung, and Blood Institute asthma guidelines. Patients with oat allergy, while rare, are to be excluded as this will serve as the placebo for our exit food challenge.

6.3 Study Assessments

The study Schedule of Activities as provided in section 1.3 of the protocol is as follows.

Visit		Study Visit 1	Study Visit 2 Visit 1 +1-4 weeks	SV 3 Visit 2 +2 weeks	SV 4 Visit 2 +4 weeks	SV 5 Visit 2 +6 weeks	SV 6 Visit 2 +8 weeks	SV 7 Visit 2 +10 weeks	SV 8 Visit 2 +12 weeks	SV 9 Visit 2 +14 weeks	SV 10 Visit 1 +18 weeks

Procedures		Enrollment/Baseline visit	Oral Food Challenge	Initial dose escalation	Dose escalation visit 1	Dose Escalation Visit 2	Dose escalation visit 3	Dose escalation visit 4	Dose escalation visit 5	Dose escalation visit 6	Dose escalation visit 7	Oral Food Challenge
Informed Consent	X											
Demographic s	X											
Vitals	X	X	X	X	X	X	X	X	X	X	X	X
Spirometry*	X		X	X	X	X	X	X	X	X	X	X
Blood Draw			X									X
Skin prick test			X									X
Oral food challenge		X										X
Urine Pregnancy	X											X
Study Drug Administratio n			X	X	X	X	X	X	X	X	X	
Study Drug Compliance				X	X							
AE Review			X	X	X	X	X	X	X	X	X	X
Conmed Assessment	X	X	X	X	X	X	X	X	X	X	X	X
FAQL Questionnaire	X											X

Due to the difficulties of scheduling study visits during the COVID-19 pandemic, the primary analysis will not place any limitations on the timing of study visits. All study visits will be analyzed in order by date, and the number of days from initial oral food challenge (OFC) and initial dose escalation visit will be reported for each study visit. If more than seven dose escalation visits are required as described in the study protocol section 6.1.1 'Study Intervention Description', the additional study visits will be named 'Additional Study Visit 9.1' through 'Additional Study Visit 9.x' for the purposes of analysis and reporting.

6.3.1 Assessment of Primary Efficacy Endpoint

The primary efficacy endpoint is 'response to treatment' defined as ability to successfully consume a single dose of 300 mg or greater of peanut protein with no dose limiting symptoms at the exit DBPCFC. This endpoint will be analyzed as a binary variable (yes response to treatment/no response to treatment).

6.3.2 Assessment of Secondary Efficacy Endpoints

Highest tolerated dose and cumulative dose. The highest dose of roasted peanut protein tolerated by the subject, cumulative total dose of roasted peanut protein tolerated by the subject, and the changes in highest tolerated dose and cumulative tolerated dose from initial OFC to the peanut protein arm of the exit DBPCFC will be analyzed as ordinal variables because of the interval nature of the dosing schedule (Chinchilli et al., 2005). The dose schedule for initial OFC and exit DBPCFC is shown below.

Peanut protein challenge dose schedule at initial (SV 1) and exit (SV 10) oral food challenges.

Oral food challenge	Highest tolerated dose of peanut protein (mg)	Cumulative tolerated dose of peanut protein (mg) at initial OFC	Cumulative tolerated dose of peanut protein (mg) at exit DBPCFC
Initial only	5	5	
Initial only	10	15	
Initial and Exit	25	40	25
Initial only	50	90	
Initial and Exit	100	190	125
Exit only	200		325
Exit only	300		625
Initial only	500	690	
Exit only	600		1225
Initial and Exit	1000	1690	2225
Initial only	4000	5690	

Serum markers of sensitization and tolerance to peanut. Changes in serum markers of sensitization and tolerance to peanut from initial dose escalation visit to final study visit will be analyzed as continuous variables.

Food Allergy Quality of Life Questionnaires (FAQQLQ). The Food Allergy Quality of Life Questionnaire – Parent Form (FAQQLQ-PF) will be used for patients aged 0-12 years (DunnGalvin et al., 2008). The Food Allergy Quality of Life Questionnaire –Teenager Form (FAQQLQ-TF) will be used for patients aged 13-17 year (Flokstra-de Blok et al., 2008). For all FAQQLQ surveys, all questions are scored on an ordered scale from 1 (“no impairment”) to 7 (“maximal impairment”) for calculations. Subscale and summary scores are calculated as item mean scores, on the same scale from 1 to 7. Subscale and summary scores, and changes in subscale and summary scores from enrollment/baseline visit to final study visit, will be analyzed as continuous variables. The MID (minimally important difference) for the FAQQLQ is 0.5 (DunnGalvin et al., 2010), and the change in total score will be dichotomized as greater than or equal to 0.5 or less than 0.5 and analyzed as a binary variable. Scoring of the FAQQLQ is detailed in section 9.3.2.

